2.7 Study Rationale

The persistence of mixed hematopoietic cell chimerism is associated with a significantly high risk of disease relapse after allogeneic HCT [13, 28-30]. Once the patient's disease has relapsed after allogeneic HCT, the likelihood for long-term survival is poor. Therefore, a strategy that can help promote conversion of mixed to complete hematopoietic cell chimerism prior to disease relapse, and does not promote significant GVHD has the potential to help improve the outcomes of allograft recipients by reducing the risk of disease relapse. The goal of the current proposed trial will be to determine if the addition of very low-dose TBI to standard TLI-ATG conditioning therapy will increase the proportion of patients with FDC at Day 28 post-transplant, without reducing tolerability or increasing transplant morbidity. We **hypothesize** that the addition of very low-dose TBI at 80 cGy to TLI-ATG will result in at least a 30% increase in the proportion of patients with FDC in the CD3 subset at Day 28 post-HCT. This study will follow a single-arm Simon 2-stage trial principle. In Simon stage 1, we will enroll 11 patients, and if 5 or fewer patients respond, defined as $\geq 95\%$ donor chimerism in the CD3 compartment at Day 28, we will stop for futility. If 6 or more respond in Simon stage 1, then in stage 2 we will continue to enroll a full sample of 20 patients and declare success if a total of 11 or more patients respond. The primary endpoint will be the determination of the rate of conversion from mixed to complete donor chimerism. Secondary endpoints will include the risk of acute and chronic GVHD, freedom from disease progression, event-free and overall survival, and the relapse rate. The goal is to improve the rate of attaining complete chimerism without increasing the risk of GVHD. If following the Simon 2-stage trial the results are encouraging, we will expand our experience to a broader trial to determine if the TLI/ATG/low-dose TBI is associated with significantly lower rates of disease relapse.

2.8 Study Design

This is a single institution open-labeled single treatment study evaluating the safety and efficacy of very low-dose TBI added to TLI-ATG conditioning in adults undergoing allogeneic HCT from related and unrelated donors. Enrollment of 20 patients is expected to be completed in less than 2 years. The study will involve a single non-randomized intervention arm of administering TBI 80 cGy on Day -1 of standard TLI ATG conditioning. The total duration of patient study participation is 12 months. Per regular medical care for HSC transplant patients, all recipients will be followed long term and tracked via the Stanford BMT patient database for overall survival; event-free survival; and late complications such as but not limited to relapse; late chronic GVHD; and infections.

3. PARTICIPANT SELECTION AND PRE-ENROLLMENT REQUIREMENTS

Inclusion and Exclusion Criteria are provided on the Eligibility Checklist, following, and which may be extracted for use in screening potential subjects.

The following Participant Eligibility Checklist will be completed in its entirety for each subject prior to registration. The completed, signed, and dated checklist will be retained in the subject's study file, and the study's Regulatory Binder.

Pursuant to Stanford Medicine SOP "Confirmation of Participant Eligibility in Clinical Trials," the treating Physician (investigator); the Study Coordinator; and an Independent Reviewer will verify that the subject's eligibility is accurate; complete; and legible in source records. A description of the eligibility verification process will be included in the EPIC or other Electronic Medical Record progress note.

Participant Eligibility Checklist

For each prospective study participant that is screened, this checklist will be printed, the results recorded, and filed in the respective subject binder or file. It is anticipated that not all prospective study participants will be enrolled.

I. Protocol Information

Protocol Title:	Very Low-dose Total Body Irradiation in Combination with Total Lymphoid Irradiation and anti-Thymocyte Globulin to Improve Donor Engraftment in Patients Undergoing Non-Myeloablative Hematopoietic Cell Transplantation
eProtocol number: OnCore number:	IRB-47407 BMT330
Principal Investigator:	[name]

II. Subject Information

Subject name / Unique ID:	/
Gender	 Male  Female

III. Study Information

3.1 Patient Inclusion Criteria (patients must have all of the following).

Prospective Participant Must MATCH ALL these Inclusion Criteria to be Eligible	Yes	No	Supporting Documentation *
1. ≥ 18 years old			
2. Has a HLA-matched or single allele-mismatched adult sibling donor or unrelated donor			
3. Has a myeloid or lymphoid malignant disease that will be treated with TLI and ATG reduced-intensity conditioning for allogeneic transplant [any of the following: acute myeloid leukemia (AML); myelodysplastic syndrome (MDS); myeloproliferative disease syndrome (MPD)]; chronic lymphocytic leukemia (CLL); B or T-cell non-Hodgkin lymphoma (NHL); Hodgkin lymphoma (HL); or chronic myelomonocytic leukemia (CMML)]			
4. Patients who due to age, pre-existing medical conditions, or, prior therapy are considered to be at high-risk for regimen-related toxicity associated with fully ablative transplant conditioning, and therefore reduced intensity conditioning is recommended. Or patients for whom RIC allograft transplant is recommended that is in keeping with standard of care in the transplant community			
5. Ability to understand and the willingness to sign a written informed consent document. Patients must have signed informed consent to participate in the trial.			

3.2 Patient Exclusion Criteria (excluded if any of the following)

Prospective Participants Must NOT Match ANY of These Exclusion Criteria	Yes	No	Supporting Documentation *
1. Uncontrolled bacterial, viral or fungal infection defined as currently taking medication and progression of clinical symptoms			
2. Progressive hemato-lymphoid malignancy despite conventional therapy			
3. Chronic myelogenous leukemia (CML)			
4. Active CNS involvement of the underlying malignancy if previously documented CNS involvement			
5. HIV-positive			
6. Pregnant or lactating			
7. Prior malignancy (EXCEPTION: diagnosed > 5 years ago without evidence of disease, OR treated ≤ 5 years ago but have a greater than 50% chance of life expectancy of ≥ 5 years for that malignancy).			

Prospective Participants Must NOT Match ANY of These Exclusion Criteria	Yes	No	Supporting Documentation *
8. Have a psychiatric disorder(s) or psychosocial circumstance(s) which in the opinion of the primary physician would place the patient at an unacceptable risk from transplant.			
9. Organ dysfunction defined as follows: 
 i. Left ventricular ejection fraction (LVEF) < 30%, or uncontrolled cardiac failure ii. Diffusing capacity of lung for carbon monoxide (DLCO) < 40% predicted iii. Total bilirubin > 3 mg/dL iv. SGOT or SGPT > 4 x ULN v. Creatinine > 2 mg/dL and an estimated creatinine clearance < 40 mL/min vi. Poorly-controlled hypertension despite multiple antihypertensive medications 			
10. Karnofsky Performance Status (KPS) < 60%			

* All subject files must include supporting documentation to confirm subject eligibility. The method of confirmation can include, but is not limited to, laboratory test results, radiology test results, subject self-report, and medical record review.

V. Statement of Eligibility

3.3 Informed Consent Process

A conference will be held with the patient and family to discuss this study and alternative treatments available for treatment of the underlying disease. All potential risks associated with the use of TLI; ATG; , low-dose TBI; immunosuppressive drugs; and allogeneic hematopoietic cell infusions will be discussed as objectively as possible. It will be explained that patients offered this protocol have an underlying malignancy that render them either at high risk of relapse or that will result in life expectancies of several months to no more than one to two years with conventional treatments. These patients would be unlikely to benefit from, or tolerate an autologous transplant, and are at high risk of early transplant mortality from conventional allogeneic transplant. Informed consent from the patient will be obtained using a form approved by the Administrative Panel on Human Subjects in Medical Research of the Stanford University Medical Center. The participant will receive a copy of the signed and dated consent document. The original signed copy of the research consent document must be retained in the subject's research file.

3.4 Study Timeline

It is expected the study will accrue 10 to 15 patients per year and therefore the target goal of 20 patients will be completed within 2 years of the study opening.

Patients will be followed for 12 months after the mobilized PBSC infusion on Day 0. Patients' End-of-Study Visit will be scheduled for approximately Day 360 post-PBSC infusion, +/- 8 weeks. Therefore, it is expected the study will be complete within 48 months of opening. Per regular medical care for HSC transplant patients, all recipients will be followed long-term and tracked via the Stanford BMT patient database for overall survival; event-free survival; and late complications such as but not limited to relapse; late chronic GVHD; and infections.

4. TREATMENT PLAN

The full procedure schedule is described in Section 7 Study Calendar.

4.1 Study Treatment Schedule

Transplant Schedule (See also Section 7 Study Calendar)

Week 1

Monday Day -11	Tuesday Day -10	Wednesday Day -9	Thursday Day -8	Friday Day -7	Saturday Day -6	Sunday Day -5
TLI 120 cGy	TLI 120 cGy	TLI 120 cGy	TLI 120 cGy	TLI 120 cGy	Rest	Rest
ATG **** 1.5 mg/kg + solumedrol 1.0 mg/kg	ATG 1.5 mg/kg + solumedrol 1.0 mg/kg					

Week 2 and beyond

Monday Day -4	Tuesday Day -3	Wednesday Day -2	Thursday Day -1 *	Friday Day 0	Saturday Day +1	Day 28 +/- 5 days	Day 56 +/- 5 days	Day 90 +/- 5 days
TLI 120 cGy	TLI 120 cGy	TLI 120 cGy	TLI 120 cGy	Mobilized PBMC				
	Start Tac 0.05 mg/kg oral BID***		TBI 80 cGy	Start MMF **				
						PB STRs	PB STRs	PB STRs

* As a guideline 5 hour interval will be provided between TLI and TBI on Day -1. No lung blocks will be used for TBI. The dose rate will be \leq 2 Gy/minute. The Pre-HCT radiation oncology consultation will include simulation for both TLI and TBI and should be scheduled as such

** MMF 15 mg/kg PO BID for matched related donors; 15 mg/kg PO q8 hours for unrelated donors (URDs) or mismatched related donors. Physician discretion can round up or round down MMF to the nearest 250m/dose.

*** Tac starting dose is a recommended guideline yet based on Physician/APP discretion this start dose can be modified, typically lowered due to concern about drug-drug interaction and possible Tac toxicity.

**** ATG dosing is based on actual weight yet if >15 kg above ideal body weight the ordering MD has the discretion to dose ATG based on actual weight or dose based on adjusted weight, both are acceptable.

4.2 Criteria for Removal from Study

All adverse events will be reviewed by Stanford Cancer Institute Data and Safety Monitoring Committee (DSMC) and patients will be removed from the study for the following reasons:

- Non-compliance with the protocol (defined as inability to receive all scheduled treatments, follow-up appointments, and tests)
- Patient request to withdraw from the study

4.3 Alternatives

Alternative therapies will be discussed with each patient and would potentially include allogeneic transplantation using TLI and ATG conditioning without TBI or allogeneic transplantation using

other transplant conditioning or other investigational therapies, or best of care non-transplantation therapy.

4.4 Compensation

There will be no compensation for participation on study.

5. ADVERSE EVENTS AND REPORTING PROCEDURES

5.1 Adverse Events

Hematopoietic cell transplantation (HCT) is an aggressive therapy for the treatment of a number of life threatening disorders, including cancer. In this setting, a very large number of Grade 1, 2 and 3 adverse events (AEs) are expected to occur, regardless of whether or not a patient is participating in a research study. In order to minimize the “background noise” and to focus on clinically significant, meaningful adverse events useful in the assessment of proposed trial the following AE reporting schema is proposed. This schema is intended to capture all AEs that are clinically significant and/or impactful, but minimize “not informative” AE collection.

- Grade 4 and higher AEs will be collected and documented with causality attribution on an adverse event log (AE log), and all AEs meeting the criteria of “serious” as defined at 21CFR§312.32(a), including any that are otherwise Grade 1, 2 or 3 will be collected; identified as serious; and documented on an AE log, including causality attribution.
 - An adverse event is considered serious if it fulfills one of the following criteria per 21CFR§312.32(a):
 - Results in death.
 - Life threatening (patient at risk of death at the time of the event).
 - Requiring new inpatient hospitalization or prolongation of existing hospitalization.
 - Resulting in persistent or significant disability.
 - Other medical events that may not be immediately life threatening or result in death or hospitalization by may jeopardize the patient or require intervention to prevent one of the outcomes listed above
- Laboratory values without a clinical consequence or outcome will not be tracked as adverse events, unless deemed serious.
- Grade 1-3 AEs not meeting these criteria will not be collected, except as follows. Grade 1 to 3 AEs resulting in subject termination or withdrawal from the study will be collected.

All Serious Adverse Events (SAEs) will be tracked until resolution or at least 60 days after the study treatment.5.2 Adverse Event Reporting

All serious adverse events (SAEs) as outlined in section above and meeting the criteria specified in 21CFR§312.32(c)(1) that occur from start of transplant conditioning through to day +90 post transplant will be collected. SAEs related to study treatment will be collected through the Week 52 follow up visit. All SAEs will be reported to in accordance with the established practices of the Stanford Division of Blood and Marrow Transplantation, as well the IRB and DSMC. The collected AEs will be documented in the adverse event log.

6. DATA CAPTURE

The Protocol Director, or his/her designee, will prepare and maintain adequate and accurate participant case histories with observations and data pertinent to the study, in accordance with the established practices of the Stanford Division of Blood and Marrow Transplantation.

The trial completed enrollment and is closed to patient accrual. The trial remains open for patient observation and determination of the trial's secondary outcomes.

Time is needed for patients to complete this period of observation. Once all the patients have passed the last time point of observation the study PI will analyze the data in context of BMT Core Group B which includes Drs. [name] and [name]. The outcomes will be uploaded to Clinical trials.gov.

There is no data specific for this trial that extends beyond what the extensive and comprehensive bmt database already collects. This data will be reviewed by the study PI and Core B for accuracy before it is finalized in BMTcore.

7. STUDY CALENDAR

	Pre-enrollment requirements		Day -11, -10, -9, -8, -7	Day -4	Day -3	Day -2	Day -1	Day 0	Day 28 +/- 7 days	Day 56 +/- 14 days	Day 90 +/- 14 days	Day 180 +/- 4 weeks	Day 360 +/- 8 weeks
	Day -180 to -13	Day -42 to -12											
Informed consent	X												
Demographics	X												
Donor evaluation	X												
B-HCG ^a		X											
Height		X											
Weight		X						X	X	X	X		
Medical history	X							X	X	X	X		
Concurrent meds		X						X	X	X	X		
Physical exam	X							X	X	X	X		
Vital signs ^b		X						X	X	X	X		
Performance status	X							X	X	X	X		
Central venous catheter		X											
Blood sample for:		↓						↓	↓	↓	↓	↓	↓
CBC w/diff		X						X	X	X	X		
Serum chemistry ^c		X						X	X	X	X		
STR analysis ^d									X	X	X	X	X
TLI ^e			X	X	X	X	X						
TAC ^f					X								
ATG ^g			X										
TBI ^h							X						
PBSC Infusion								X					
MMF ⁱ								X					
SAE evaluation								X - Weekly from Day 0 through Day 90					
Disease Status Assessment ^j	X									X	X as indicated	X as indicated	

- a: Pregnancy test for women of childbearing potential only.
- b: Temperature, blood pressure, and pulse.
- c: Albumin, alkaline phosphatase, total bilirubin, calcium, chloride, creatinine, glucose, potassium, total protein, AST, ALT, sodium
- e: TLI: Total lymphoid irradiation, 120 cGy.
- f: TAC: Tacrolimus
- g: ATG: Anti thymocyte globulin, 1.5 mg/kg with solumedrol 1.0 mg/kg.
- h: TBI: Total body irradiation, 80 cGy.
- i: MMF: Mycophenolate mofetil, by mouth.
- j: Response assessment as per disease histology, and may include CT, PET, and/or MRI imaging, and bone marrow biopsy or aspiration (refer to Appendix B), and is typically performed around Day 90 post-transplant (Day 0).
- k: Short tandem repeat (STR) analysis (by comparison to subject's pre-study HLA analysis) on Day 28 +/- 7 days; Day 56 +/- 14 days; Day 90 +/- 14 days; Day 180 +/- 4 weeks; Day 360 +/- 4 weeks, and thereafter as per standard of care.

8. MEASUREMENTS and STATISTICAL METHODS

Our extensive experience with the TLI ATG conditioning for allogeneic HCT in cancer patients showed a 30 to 40% incidence of FDC at Day 90, with a 95% confidence interval of 10 to 49%. The non-relapse mortality (NRM) was 3% (95% CI: 0 to 14%) at 100 days and 6% (95% CI: 1 to 28%) at 1 year. The incidence of acute GVHD by Day 100 was 6% (0.7 to 22%).

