10. STATISTICAL CONSIDERATIONS

10.1 Statistical Analysis

The sample size determination for the clinical trial will follow a single arm Simon 2-stage trial principle. The null hypothesis that the true response is $p_u = 0.40$ will be tested against a one-sided alternative ($p_d = 0.7$). In the first stage, $n_1 = 11$ patients will be accrued. If there are $r = 7$ or fewer responses in these $n_1 = 11$ patients, the study will be stopped. Otherwise, $n - n_1 = 9$ additional patients will be accrued for a total of $n = 20$. The null hypothesis will be rejected if $r + 1 = 11$ or more responses are observed in $n = 20$ patients. This design yields a type I error rate of $\alpha = 0.10$ and power of $1 - \beta = 0.90$ when the true response rate is $p_d = 0.70$.

We plan to use a dose of 80 cGy of TBI on Day -1 of HCT. It is fully expected that this low-dose will be safe and not provoke or increase the risk of GVHD or other complications. Patients will be evaluated for toxicities, defined as new Grade 3 to 4 toxicities, according to the Common Terminology Criteria for Adverse Events (CTCAE) v.5 and Grade 3 to 4 GVHD (Appendix A) during the 90 days following HCT.

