10.2 Stopping Rule

Based on preclinical data, we do not believe the TBI at such a low-dose will aggravate GVHD, and we do not expect additional regimen-related toxicities at this dose. Patients will not be enrolled into Stage 2 until all patients in Stage 1 have reached 90 days post-transplant. Patients will not be enrolled into Stage 2 until all patients in Stage 1 have reached 90 days post-transplant.

The study will be terminated if the number of subjects who experience a "stopping event" (defined as Grade 4 GVHD) is 2, 3 or 4 among (respectively) the first 6, 12, or 18 patients. This rule is based on stopping if the lower 80% confidence limit for the true probability of a "stopping event"

exceeds 12% (the maximal acceptable rate) at any look. The rule is implemented with a forward-looking interpretation, so that if the number of events hits the boundary for the current look at any time, the study will stop. Subjects will not be enrolled into Stage 2 until all subjects in Stage 1 have reached 90 days post-transplant without triggering the stopping rule, and enrollment will be delayed if necessary at each stopping rule milestone, to ensure that subject 7, 13, and 19 are not enrolled until the stopping rule at (respectively) 6, 12, and 18 is cleared (for example, if there has been one stopping event in the first 5 subjects, enrollment is paused until patient 6 reaches 90 days without an event).

The stopping rule described above, which we have used in many studies, controls the "false alarm" rate. We do not generally calculate the "true alarm rate" at probabilities exceeding the max acceptable rate, because we do not think it is informative. It is well-understood that the small samples in phase 1 and 2 generally do not provide precise upper bounds for the probability of unwanted effects, so the purpose of stopping rules is to protect the patients enrolled in the study, as far as possible, consistent with the inherent risks of early phase studies and the potential benefit. If the stopping rule is not triggered even though the true risk is substantially greater than the max acceptable rate, then the actual harm has been limited to the extent possible in an early phase trial.

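### The study calendar schedules SAE evaluation only from Day 0 to Day 90, although Section 5.2 requires collection from the start of conditioning and, for treatment-related SAEs, to Week 52

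*Combined protocol and SAP*

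**What the plan says.** Section 5.2 (Adverse Event Reporting) sets the collection window. SAEs "that occur from start of transplant conditioning through to day +90 post transplant will be collected", and beyond that "SAEs related to study treatment will be collected through the Week 52 follow up visit". The transplant schedule in Section 4.1 puts the first conditioning day at Day -11. Section 2.8 describes the intervention as "administering TBI 80 cGy on Day -1 of standard TLI ATG conditioning".

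The SAE row of the Section 7 calendar reads "Weekly from Day 0 through Day 90". Nothing is marked for SAEs in the Day -11 to Day -1 columns, or at Day 180 and Day 360.

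Section 5.1 deals with how long a recorded event is followed: "All Serious Adverse Events (SAEs) will be tracked until resolution or at least 60 days after the study treatment".

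Section 10.1 evaluates toxicity and Grade 3 to 4 GVHD "during the 90 days following HCT". Section 10.2 uses the same horizon for the Grade 4 GVHD stopping rule; in its worked example, "enrollment is paused until patient 6 reaches 90 days without an event".

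**The concern.** The calendar is more than a summary. Section 4 refers to it for the full procedure schedule, Section 8.1 ties toxicity monitoring to it, and Section 9.3 has the data team collect what it requires. A coordinator working from it would make the first SAE check after all the TLI, the ATG and the study TBI have been given, and the last one at Day 90.

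The early gap matters because it contains the delivery of the tested component. Under Section 4.2, a patient who cannot receive all scheduled treatment is removed from the study. A patient whose SAE during conditioning prevents infusion would therefore never reach the Day 0 check, nor the toxicity window of Section 10.1, which opens at transplant. The late gap matters because related SAEs are due to be collected for most of the year with no scheduled prompt.

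The synopsis sets out to show better chimerism without loss of tolerability, in a single arm. Any SAE that is missed lowers the toxicity count. The follow-up wording in Section 5.1 raises a smaller issue: the final outcome of some recorded SAEs may never be documented.

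**Working it through.** The plan gives no figure of its own on this point, so the check is a comparison of windows with day arithmetic.

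**Inputs**
- First conditioning day: Day -11 (Section 4.1).
- TBI: Day -1 (Sections 2.8 and 4.1). Infusion: Day 0.
- All-SAE collection: start of conditioning to Day +90 (Section 5.2).
- Related-SAE collection: to Week 52 (Section 5.2).
- Scheduled SAE evaluation: weekly, Day 0 to Day 90 (Section 7).
- Tracking of a recorded SAE: to resolution, or a minimum of 60 days after study treatment (Section 5.1).
- Stopping-rule and toxicity horizon: 90 days after transplant (Sections 10.1 and 10.2).

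**Start of the window**
- Required but unscheduled: Day -11 to Day -1 = 11 days (nine TLI days and two rest days).
- Whole all-SAE window: 90 - (-11) + 1 = 102 days.
- Share: 11 / 102 = 10.8%.
- No other calendar row fills the gap. The Day -11 to Day -1 columns list treatments only, with no history, examination, vital signs or laboratory tests.

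**End of the window, related SAEs**
- Week 52 = 52 × 7 = Day 364.
- Gap after the last scheduled evaluation: 364 - 90 = 274 days, or 360 - 90 = 270 days to the nominal Day 360 visit.

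**Minimum tracking time**
- Section 5.1 does not say which treatment day starts the count. From TBI: -1 + 60 = Day 59. From infusion: 0 + 60 = Day 60.
- Distance to Day 90: 90 - 59 = 31 days, or 90 - 60 = 30 days.
- An SAE that starts after that point is collected, but the 60-day alternative has already expired, so no minimum follow-up applies to it.

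**Does the 60-day text affect the stopping rule?**

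| Provision | What it governs | Runs to |
|---|---|---|
| Section 5.1, tracking sentence | Follow-up of an SAE already recorded | Resolution, or at least about Day 59 or 60 |
| Section 5.1, Grade 4 and higher AEs | Which AEs are recorded | No link to the 60-day sentence |
| Section 5.2 | Which SAEs are collected | Day 90 (Week 52 if related) |
| Section 7 | When SAEs are looked for | Day 90, weekly |
| Section 10.2 | Clearance of the stopping rule | Day 90 |

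The provisions that govern finding a Grade 4 GVHD event do not depend on the 60-day sentence, and Sections 5.2, 7 and 10.2 agree on Day 90. If Grade 3 GVHD were closed as an SAE at Day 59 and progressed to Grade 4 before Day 90, it would still be caught.

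**The case against.** The strongest reply is that Section 5.2 settles the matter. A death or hospitalisation during conditioning is reportable whatever the visit grid shows. Section 5.1 also collects Grade 4 and higher events, and lower-grade events that lead to withdrawal, without naming a start day. Patients attend for radiation on all nine TLI days, and the Day 0 visit, one day after TBI, includes an SAE evaluation, history, examination and laboratory tests. This stands as far as it goes: the events are inside the plan. It does not remove the mismatch, because the calendar is what staff are told to work from and it does not prompt for these events.

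A reader might infer that the 60-day text contradicts the 90-day windows, or that it undermines the stopping rule. The documents support neither reading. Section 5.1 sets a minimum for following a recorded event, which is a different quantity from the period of collection, and the stopping event is ascertained by other provisions to Day 90.

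A reader might also take the Section 10.1 window as a further conflict. It is not an SAE collection window; it defines a toxicity evaluation period after transplant. Starting it earlier would be a design preference, not a reconciliation.

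Finally, Section 6 says that enrolment is complete, so changing the calendar cannot add checks during conditioning. That is correct, and it changes what the fix can achieve.

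**Conclusion.** The concern holds for the calendar. Section 5.2 and Section 7 disagree at both ends: 11 days before infusion (10.8% of the 102-day all-SAE window) and 270 to 274 days after Day 90 for related SAEs have required collection but no scheduled evaluation. The consequence is a risk of under-ascertainment. These are counts of days, not of events. The documents do not show that any SAE was missed, so a favourable bias in the safety summary is possible but not demonstrated.

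On Section 5.1 the point is narrower. The wording allows an unresolved SAE to be closed about 30 days before all-SAE collection ends, and it leaves later-onset events with no follow-up minimum. Day 59 assumes that study treatment means TBI; Day 60 assumes the infusion.

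No sample size, error rate, power or stopping boundary changes. The issue should be corrected before results are posted, but it does not threaten the primary analysis.

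**What to change.** 1. **Section 7.** Make the SAE row match Section 5.2: start at Day -11, continue weekly through Day 90, then evaluate related SAEs at the Day 180 and Day 360 visits.
2. **Section 5.1.** Define follow-up per event: track each SAE to resolution or stabilisation or, if it is unresolved, to the end of its Section 5.2 collection window (Day 90, or Week 52 if related).
3. **Safety summary.** State that SAEs from Day -11 to Day -1 are included. Moving the Section 10.1 toxicity window is optional and, at this stage, would be post hoc.
4. **Record review.** Because accrual is closed, check source records and the BMT database, before results are posted, for SAEs during conditioning, related SAEs after Day 90, and the outcomes of SAEs closed unresolved.

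The amendment covers one calendar row and a few sentences. The Day 180 and Day 360 time points already exist for STR sampling. The real cost is limited record review and slightly more SAE data entry. For conditioning, the review can recover only what was documented at the time.
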